12. DATA SUBMISSION SCHEDULE

Case report forms with appropriate source documentation will be completed according to the following schedule:

Table 7: Data Submission Schedule

Case Report Form	Submission Schedule
Original Consent Form	Prior to registration
Registration Form	
Eligibility Form	Prior to starting treatment
On-Study Form	
Treatment Summary Form for TTFields	Every 4 weeks until completion of treatment
Treatment Summary Form for Pembrolizumab	Every 3 weeks while patient is on cycle
Treatment Summary Form for Temozolomide	Every 4 weeks while patient is on cycle
MRI Form	Baseline and every 2 months thereafter until
	completion of treatment
KPS Form	
Physical Exam Form	Per Study Calendar
Lab result	
Adverse Events Form	As per Section 9.0
End of Treatment Form	30 days after completion of treatment.
Survival Information	Every 3 months after completion of study
	therapy.

13. RESPONSE EVALUATION

For the purposes of this study, patients should be re-evaluated for response every 2 months +/- 7 Days. In addition to a baseline scan, confirmatory scans should also be obtained 2 months +/- 7 days following initial documentation of objective response. If a patient develops symptoms that are potentially indicative of disease progression, scans may be done sooner than every 8 weeks as per standard practice discretion.

Response and progression will be evaluated in this study using the updated response assessment criteria for high-grade gliomas: Response Assessment in Neuro-Oncology (RANO) [65] prior to pembrolizumab and Immunotherapy RANO (iRANO) working group guidelines once pembrolizumab has started [64] with minor modifications.

The goal of treatment compliance for this study is wearing the system for an average of no less than 75% of the time over a 4-week period for as many months as possible. Compliance reports with Optune will be obtained by Novocure's DSS per usual procedures. If a patient's compliance is below 50% over the first and second 4-week periods consecutively from the start of treatment, the patient will be trained on the importance of compliance and any barriers to compliance will be addressed. If a patient's compliance is still below 50% in the third 4-week period, the patient will be removed from study and that subject should be considered non-evaluable for survival analysis

and should be replaced. This subject however should remain evaluable for the toxicity and tolerability endpoints as per end of treatment requirement detailed in section 6.6.

13.1 Criteria for Determining First Progression Depending on Time from Initial Chemoradiotherapy

Table 8: RANO and iRANO Criteria for Determining First Progression

First Progression	Definition
Progressive disease < 12 weeks after completion of chemoradiotherapy	Progression can only be defined using diagnostic imaging if there is new enhancement outside of the radiation field (beyond the high-dose region or 80% isodose line) or if there is unequivocal evidence of viable tumor on histopathologic sampling (e.g., solid tumor areas [i.e., > 70% tumor cell nuclei in areas], high or progressive increase in MIB-1 proliferation index compared with prior biopsy, or evidence for histologic progression or increased anaplasia in tumor). Note: Given the difficulty of differentiating true progression from pseudoprogression, clinical decline alone, in the absence of radiographic or histologic confirmation of progression, will not be sufficient for definition of progressive disease in the first 12 weeks after completion of concurrent chemoradiotherapy.
Progressive disease ≥ 12 weeks after chemoradiotherapy completion	 New measurable contrast-enhancing lesion on decreasing, stable, or increasing doses of corticosteroids. Increase by ≥ 25% in the sum of the products of perpendicular diameters between the first postradiotherapy scan, or a subsequent scan with smaller tumor size, and the scan at 12 weeks or later on stable or increasing doses of corticosteroids. Clinical deterioration not attributable to concurrent medication or comorbid conditions is sufficient to declare progression on current treatment but not for entry onto a clinical trial for recurrence. For patients receiving antiangiogenic therapy, significant increase in T2/FLAIR nonenhancing lesion may also be considered progressive disease. The increased T2/FLAIR must have occurred with the patient on stable or increasing doses of corticosteroids compared with baseline scan or best response after initiation of therapy and not be a result of comorbid events (e.g., effects of radiation therapy, demyelination, ischemic injury, infection, seizures, postoperative changes, or other treatment effects).

Note: RANO guidelines will be applied prior to first pembrolizumab infusion. After pembrolizumab treatment has been initiated, iRANO will be applied as described in Sections 13.4 and 13.5

13.2 Disease Parameters

Measurable disease: Bi-dimensionally measurable lesions with clearly defined margins by MRI scan of ≥ 10 mm. All tumor measurements must be recorded in millimeters (or decimal fractions of centimeters).

Non-measurable or evaluable disease: Uni-dimensionally measurable lesions or lesions with margins not clearly defined such as areas of T2/FLAIR signal abnormality or poorly defined enhancing abnormality.

Note: For cystic lesions, the only measurable part is any enhancement area around the cyst that is clearly defined and bi-dimensionally measurable. The cyst itself should not be considered measurable or non-measurable disease.

Target lesions: All measurable lesions that are seen at baseline MRI. Target lesions should be selected on the basis of their size (lesions with the longest diameter), but in addition should be those that lend themselves to reproducible repeated measurements. It may be the case that, on occasion, the largest lesion does not lend itself to reproducible measurement in which circumstance the next largest lesion, which can be measured reproducibly should be selected. When there are too many measurable lesions, choose the largest 3 lesions as target lesions to follow. The other measurable lesions should be considered evaluable for the purpose of objective status determination.

Non-target lesions: All non-measurable lesions should be identified as non-target lesions and should also be recorded at baseline. Measurements of these lesions are not required, but the presence, absence, or in rare cases unequivocal progression of each should be noted throughout follow-up.

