10.3 Sample Size Considerations

To determine if the proposed sample size of 24 patients enrolled in the triple combination arm will allow us to detect a clinically relevant improvement in median PFS relative to the median PFS of 6.7 months observed in the historical control arm, we assumed an accrual period of 12 months, an accrual rate of 2 patients per month, an additional 18 months of follow-up after the end of accrual, and proportional hazards. After confirming that the Weibull distribution could reasonably be used to characterize PFS times in the historical control arm, we estimated the Weibull shape parameter k from the historical control PFS curve. The shape parameter k determines if the hazard rate underlying a survival curve is accelerating over time (k>1), constant over time (k=1; identical to exponential survival), or decelerating over time (k<1). Based on a shape parameter estimate of k=0.88 with empirical 95% confidence interval (0.82,0.95) obtained via simulation of the historical control data, our proposed sample size of 24 patients in the triple combination arm should allow us to detect in improvement in PFS of 6 to 8 months with 80% power and a 1-sided significance level of 0.05 (detectable effect size methodology from Wu and Xiong, 2014 [69]).

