13.4.2 Partial Response

Decrease of ≥50% compared with baseline in the sum of products of perpendicular diameters of all target lesions that are sustained for at least 4 weeks; no new measurable lesions; stable or improved T2/FLAIR; stable or decreased steroid dose; clinically stable or improved.

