13.4.4 Progressive Disease

At least a 25% increase in the sum of products of perpendicular diameters of at least 1 target lesion, taking as reference the smallest sum of products of perpendicular diameters on study (this includes the baseline sum if that is the smallest on study). The absolute increase in any dimension must be at least 5mm when calculating the products of perpendicular diameters.; or new measurable lesions; or substantial worsened T2/FLAIR; or substantial clinical decline that is a direct cause of the tumor and cannot be attributable to a non-tumor cause.

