13.6 Response Evaluation after a Complete Resection

A complete resection will be defined as contiguous contrast enhancement < 1cm in 2 perpendicular measurements in each of 2 perpendicular planes (i.e., axial and coronal). Because neither the RECIST [70] nor MacDonald [71] criteria are completely appropriate for patients with minimal residual disease, a modified version of these criteria will be used as outlined below.

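### Section 13.2 has sites record unequivocal progression of non-target lesions, but the progression rule in force after pembrolizumab starts (13.4.4) does not say whether it counts as a PFS event

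*Combined protocol and SAP*

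**What the plan says.** - **What is recorded.** Section 13.2 classes every non-measurable lesion as non-target. Measurements of these lesions are optional, but "in rare cases unequivocal progression of each should be noted throughout follow-up". When there are too many measurable lesions, three become targets, and "The other measurable lesions should be considered evaluable for the purpose of objective status determination".
- **What counts as progression after pembrolizumab starts.** The note to Table 8 hands over to 13.4 and 13.5 at the first infusion. Section 13.4.4 opens with "At least a 25% increase in the sum of products of perpendicular diameters of at least 1 target lesion", then lists a new measurable lesion, substantially worse T2/FLAIR, and substantial clinical decline due to tumor. Table 9 adds timing and confirmation rules but no non-target criterion.
- **What counts as response.** Partial response (13.4.2) needs a decrease of at least 50% in "all target lesions that are sustained for at least 4 weeks; no new measurable lesions", with T2/FLAIR, steroid dose and clinical state stable or better. It sets no condition on non-target enhancing disease.
- **The one broader rule.** Section 13.6.4 counts growth of any enhancing tumor, but only after complete resection: "A complete resection will be defined as contiguous contrast enhancement < 1cm in 2 perpendicular measurements in each of 2 perpendicular planes".

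**The concern.** PFS is the primary endpoint, tested in one open-label arm of 24 patients against a fixed historical curve. The plan collects a progression finding and gives it no consequence. Two readers following the text could date the same event differently. A reader who applies 13.4.4 literally will score enhancing growth outside the target lesions as stable disease, or as partial response if the target shrank. The PFS event then waits for another criterion to be met. A later date can only lengthen PFS in this arm, which is the direction of the study hypothesis. Radiographic response, a secondary endpoint, is exposed in the same way.

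**Working it through.** **1. Which rule governs.** Adjuvant treatment starts 4 to 6 weeks after chemoradiation, and the study calendar puts the first pembrolizumab dose at week 4. That is 4+4 = 8 to 6+4 = 10 weeks after chemoradiation. On the planned schedule 13.4.4 therefore takes over before the row of Table 8 for 12 weeks or later comes into play.

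**2. Who is left uncovered.** Sections 13.2 and 13.3 require clear margins and at least 10 mm in both diameters for measurability. Section 13.6 requires under 1 cm in both directions for complete resection. Between the two lies, for example:

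| Residual enhancement at baseline | Measurable (13.2/13.3)? | Complete resection (13.6)? | Size-based progression rule |
|---|---|---|---|
| 20 x 4 mm rim | No, 4 mm is under 10 mm | No, 20 mm is over 1 cm | None explicit |
| Ill-defined area of 1 cm or more | No, margins unclear | No | None explicit |

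Such patients can enrol, since 4.1 allows biopsy only. If the rim grew to 30 x 25 mm, the product would go from 80 to 750 mm², yet it is neither a target lesion nor plainly a new one. A patient who also has a target lesion is in the same position for growth confined to non-target disease.

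**3. The plan's own figure.** Inputs from 10.3: "proposed sample size of 24 patients enrolled in the triple combination arm"; control "median PFS of 6.7 months observed in the historical control arm"; recruitment of 2 a month over 12 months; 18 further months of follow-up; Weibull shape k = 0.88 (0.82 to 0.95); one-sided 0.05; 80% power. With HR = (6.7/m1)^k and D the expected events under the alternative, power = Φ(√D·|ln HR| − 1.645).

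- k = 0.88: m1 = 6.7 + 6.8 = 13.5, HR = 0.540, D = 16.3. √16.3 × 0.6155 = 2.49, less 1.645 = 0.84, and Φ(0.84) = 0.80.
- k = 0.82 and 0.95: detectable improvements of 7.8 and 5.9 months.

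This reproduces the stated 6 to 8 months, which the present point does not affect.

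**4. Sensitivity of the test level.** One-sample log-rank trials were simulated under no effect (control median 6.7, k = 0.88, n = 24, uniform accrual over 12 months plus 18 months). A share f of patients had the event dated d months late, with d = 2 or 4, that is one or two MRI intervals. Z = (E − O)/√V was rejected above 1.645. The plan does not state V, so both usual choices are shown.

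| f | V = (O+E)/2, d = 2 to 4 | V = E, d = 2 to 4 |
|---|---|---|
| 0 | 0.051 | 0.038 |
| 2% | 0.053-0.055 | 0.039-0.041 |
| 5% | 0.055-0.060 | 0.041-0.045 |
| 10% | 0.061-0.071 | 0.044-0.052 |

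Repeat runs agree to within about 0.002. At f = 10% the apparent median moves from 6.7 to between 6.9 and 7.2 months. These figures assume that the EF-14 curve counted such growth on time and that every affected patient has the full delay. Neither assumption can be checked from the documents.

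**The case against.** **The gap is narrower than it looks.** A reader might infer that no growth of non-measurable enhancing tumor is ever a radiographic event. The documents do not support that. Section 13.6.4 covers complete-resection patients, 13.4.4 covers non-enhancing disease through T2/FLAIR, and the under-12-week row of Table 8 counts new out-of-field enhancement of any size. Clinical decline and death always end PFS, and 13.4 allows biopsy when findings are equivocal. All of this stands.

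**Newly measurable might mean new.** The new-measurable-lesion criterion could be read to include a baseline lesion that becomes measurable. The text does not settle this. The reading would also help fully only later, because 13.4 says that new lesions alone do not define progression in the first 6 months of immunotherapy.

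**The cited criteria may fill the gap.** Section 13 adopts RANO and iRANO with minor modifications. Whether those sources score non-target progression cannot be checked here, and the note to Table 8 sends the reader to 13.4 and 13.5 as written.

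**Rarity.** Section 13.2 itself calls these cases rare. Shares of 20% or 30% would give levels of up to about 0.096 or 0.127 with variance (O+E)/2, but nothing in the documents supports shares that large. Surplus measurable lesions will also be few, since 4.2 excludes multifocal glioma.

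**Conclusion.** The drafting gap is real and concerns the primary endpoint. After pembrolizumab starts, unequivocal progression of a non-target enhancing lesion is recorded without being scored in patients outside the 13.6 definition, and 13.4.2 can allow partial response on the same scan if its other conditions are met. The effect is a later event date in this arm.

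A reader might go further and conclude that PFS is biased upward against the control. That requires EF-14 to have counted such growth when it appeared, and the documents give no EF-14 progression criteria. If EF-14 used an equally silent rule, the delay would be in both curves.

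The size is unknown. For 2% to 10% of patients scored 2 to 4 months late, the one-sided level would be 0.053-0.071 against a base of about 0.051, or 0.039-0.052 against about 0.038, depending on the variance. With variance E it stays at or below nominal over nearly all of that range. This is a sensitivity range under the stated assumptions and not an estimate. The change is worth making because it settles how a primary-endpoint event is scored and costs little.

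**What to change.** 1. Add to 13.4.4: *or unequivocal progression of a non-target enhancing lesion, including surplus measurable lesions and a baseline non-measurable lesion that becomes measurable*. Apply the existing 13.4 rules on confirmation and backdating.
2. Add to 13.4.2 and 13.4.3: *no unequivocal progression of non-target lesions*.
3. State that patients with no target lesion who do not meet the 13.6 definition are scored by this criterion.
4. Add no new numeric threshold. Section 13.2 does not require non-target measurements, so a size rule would need data that sites need not collect.
5. Before finalizing, check the wording against the progression criteria behind the EF-14 control curve, so that both sides of the comparison count the same events.

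**Cost.** Wording only. Section 13.2 already has sites note the finding, and the Appendix B form already has non-target rows with enhancing status. The downside is that some PFS events will be dated earlier and that the criterion rests on reader judgement.

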For progressive imaging changes that occur more than 6 months from starting immunotherapy and if there is no new or substantially worsened neurological deficits that are not due to comorbid events or concurrent medications, and adjunct imaging tests such as perfusion/CBV and/or brain FDG-PET and/or amino-acid PET suggest a predominant treatment-induced effect, study treatment may continue and confirmation of disease progression status should be performed on follow-up imaging 2-3 months after initial radiographic progression. If follow-up imaging confirms disease progression, the date of actual progression should be backdated to the date of initial radiographic progression.

In the event of surgical intervention for clinical reasons of a radiographically suspicious lesionand then subsequent surgical pathology demonstrates treatment related changes with no obvious progression of tumor, the subject will be deemed not progressed and allowed to resume study treatment as assigned prior to the surgery at a time deemed safe by the treating physician, but no later than 8 weeks from the surgery.

13.4.1 Complete Response

Disappearance of all enhancing disease for \geq 4 weeks; no new lesions; stable or improved T2/FLAIR; no more than physiological steroids; clinically stable or improved.

13.4.2 Partial Response

Decrease of ≥50% compared with baseline in the sum of products of perpendicular diameters of all target lesions that are sustained for at least 4 weeks; no new measurable lesions; stable or improved T2/FLAIR; stable or decreased steroid dose; clinically stable or improved.

13.4.3 Stable Disease

Does not quality for complete response, partial response, or progressive disease; no new lesions; stable or improved T2/FLAIR; stable or decreased steroid dose; clinically stable or improved.

13.4.4 Progressive Disease

At least a 25% increase in the sum of products of perpendicular diameters of at least 1 target lesion, taking as reference the smallest sum of products of perpendicular diameters on study (this includes the baseline sum if that is the smallest on study). The absolute increase in any dimension must be at least 5mm when calculating the products of perpendicular diameters.; or new measurable lesions; or substantial worsened T2/FLAIR; or substantial clinical decline that is a direct cause of the tumor and cannot be attributable to a non-tumor cause.

13.5 Modified iRANO Criteria

Table 9: Key Considerations for modified iRANO

- a. A repeat scan is needed to confirm radiographic progressive disease for patients without significant decline if ≤ 6 months after the start of immunotherapy.
- b. The minimum time interval for confirmation of disease progression for patients without significant decline is $\geq 2-3$ months per iRANO.
- c. Further immunotherapy treatment is allowed ≤ 6 months after start of immune therapy after initial radiographic progressive disease (if clinically stable) pending disease progression confirmation.
- d. A new measurable lesion defines progressive disease if occurring > 6 months after the start of immunotherapy, unless adjunct imaging is consistent with predominant treatment effects and there are no worsened neurological deficits that are not due to comorbid events or concurrent medications.

13.6 Response Evaluation after a Complete Resection

A complete resection will be defined as contiguous contrast enhancement < 1cm in 2 perpendicular measurements in each of 2 perpendicular planes (i.e., axial and coronal). Because neither the RECIST [70] nor MacDonald [71] criteria are completely appropriate for patients with minimal residual disease, a modified version of these criteria will be used as outlined below.

13.6.1 Complete Response

Complete disappearance of enhancing tumor on consecutive CT or MRI images at least 1 month apart, and neurologically stable or improved and at the same or a lower steroid dose. To be assigned a status of "Complete Response" as a best overall response, changes in tumor measurements must be confirmed by repeat assessments that should be performed no less than 4 weeks after the criteria for response is first met.

13.6.2 Partial Response

Partial response is not assessable in patients without sufficient measurable disease.

13.6.3 Stable Disease

Insufficient change to qualify for Complete Response or Progressive disease.

13.6.4 Progressive Disease

At least a 25% increase in the longest diameter on an axial image of any enhancing tumor on consecutive CT or MRI images with a minimum of \geq 5mm of contiguous contrast enhancement in 2 perpendicular measurements in each of 2 perpendicular planes (i.e., axial and coronal).

13.6.5 Not Assessable

Progression has not been documented and one or more sites have not been assessed.

14. QUALITY CONTROL AND QUALITY ASSURANCE

14.1 Data and Safety Monitoring Plan

14.1.1 Data Monitoring Plan

Adverse events meeting the definition of an SAE and any grade 2 or greater AEs where there is a possible, probable or definite relationship between the AE and investigational drug must be reported to the Investigator within 24 hours of discovery. These will be assessed and reported to the IRB, DISC and FDA as required by policy and/or regulation.

The UFHCC SRMC conducts initial review of IITs and determines the level of risk which corresponds with DISC review requirements. The UFHCC DISC will conduct monitoring and audit activities as outlined in the DISC Charter. The results of such activities will be provided to the PI and IRB.

The UF study team will conduct annual QA self-assessments that include review of regulatory documentation (e.g., IRB documentation, FDA IND records, IND Sponsor-Investigator responsibilities), recruitment procedures, informed consent process/form documentation, subject selection, AE and SAE reporting, CRF and source documents.

14.1.2 Data Safety Monitoring Board

Oversight and monitoring of study related activities such as the safety of research participants, appropriateness of the study, and integrity of the data, will be provided by the University of Florida Health Cancer Center DSMB, now called the Data Integrity and Safety Committee (UFHCC DISC). DSMB reports will be submitted to the IRB per local policy.

